## 7.4.1 Principal Investigator/Research Team

The clinical research team consisting of the PI, LAI, research nurse and data manager will meet on a weekly basis when patients are being actively treated on the trial to discuss each patient, data acquisition, approve CRFs for data entry and address any other logistical issues pertinent to the integrity of the protocol implementation and data management.

All data will be collected in a timely manner and reviewed by the Principal Investigator or a lead associate investigator. Events meeting requirements for expedited reporting as described in Section 7.2.1 will be submitted within the appropriate timelines.

The Principal Investigator will review adverse event and response data on each participant to ensure safety and data accuracy. The Principal Investigator will personally conduct or supervise the investigation and provide appropriate delegation of responsibilities to other members of the research staff.

## 8 SPONSOR PROTOCOL/SAFETY REPORTING

## 8.1 **DEFINITIONS**

## 8.1.1 Adverse Event

Any untoward medical occurrence in a patient or clinical investigation subject administered a pharmaceutical product and which does not necessarily have a causal relationship with this treatment. An adverse event (AE) can therefore be any unfavorable and unintended sign (including an abnormal laboratory finding), symptom, or disease temporally associated with the use of a medicinal (investigational) product, whether or not related to the medicinal (investigational) product (ICH E6 (R2)).

## 8.1.2 Serious Adverse Event (SAE)

An adverse event or suspected adverse reaction is considered serious if in the view of the investigator or the sponsor, it results in any of the following:

- Death,
- A life-threatening adverse event (see Section 8.1.3)
- Inpatient hospitalization or prolongation of existing hospitalization
  - A hospitalization/admission that is pre-planned (i.e., elective or scheduled surgery arranged prior to the start of the study), a planned hospitalization for pre-existing condition, or a procedure required by the protocol, without a serious deterioration in health, is not considered a serious adverse event.

- A hospitalization/admission that is solely driven by non-medical reasons (e.g., hospitalization for patient or subject convenience) is not considered a serious adverse event.
- Emergency room visits or stays in observation units that do not result in admission to the hospital would not be considered a serious adverse event. The reason for seeking medical care should be evaluated for meeting one of the other serious criteria.
- Persistent or significant incapacity or substantial disruption of the ability to conduct normal life functions
- A congenital anomaly/birth defect
- Important medical events that may not result in death, be life-threatening, or require hospitalization may be considered a serious adverse drug experience when, based upon appropriate medical judgment, they may jeopardize the patient or subject and may require medical or surgical intervention to prevent one of the outcomes listed in this definition.

## 8.1.3 Life-threatening

An adverse event or suspected adverse reaction is considered "life-threatening" if, in the view of either the investigator or sponsor, its occurrence places the patient or subject at immediate risk of death. It does not include an adverse event or suspected adverse reaction that, had it occurred in a more severe form, might have caused death. (21CFR312.32)

## 8.1.4 Severity

The severity of each Adverse Event will be assessed utilizing the CTCAE version [X].

## 8.1.5 Relationship to Study Product

All AEs will have their relationship to study product assessed using the terms: related or not related.

- Related There is a reasonable possibility that the study product caused the adverse event. Reasonable possibility means that there is evidence to suggest a causal relationship between the study product and the adverse event.
- Not Related There is not a reasonable possibility that the administration of the study product caused the event.

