## 3.7 DURATION OF FOLLOW- UP

Patients will be followed for 6 months total after discontinuing clobetasol oral rinse treatment every 3 months by telephone or in-person interview to assess duration of treatment response, recurrence of oral GVHD, survival and resolution of any side-effects. Patients removed from treatment for unacceptable adverse events will be followed until resolution or stabilization of the adverse event. Once there is resolution of adverse events, patients will be removed from study. Patients who become unavailable within 6 months of completing treatment will not be followed beyond the terminating event. Only adverse events at least possibly related to study treatment will be collected during the follow-up period.

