## **6 DATA COLLECTION AND EVALUATION**

## 6.1 DATA COLLECTION

## 6.1.1 Data Collection

The PI will be responsible for overseeing entry of data into a 21 CFR Part 11-compliant data capture system provided by the NCI CCR and ensuring data accuracy, consistency and timeliness. The principal investigator, associate investigators/research nurses and/or a contracted data manager will assist with the data management efforts. Primary and final analyzed data will have identifiers so that research data can be attributed to an individual human subject participant.

**End of study procedures:** Data will be stored according to HHS, FDA regulations and NIH Intramural Records Retention Schedule as applicable.

**Loss or destruction of data:** Should we become aware that a major breech in our plan to protect subject confidentiality and trial data has occurred, the IRB will be notified.

Grade I AEs will only be recorded if they are deemed possibly, probably or definitely related to the study intervention.

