## 7.4 NIH REQUIRED DATA AND SAFETY MONITORING PLAN

Serious adverse events potentially attributable to the study medication or procedures will be reported to IRB. If trends are noted and/or risks warrant it, accrual will be interrupted and/or the protocol and/or consent document will be amended accordingly.

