## 8.2 Assessment of Safety Events

AE information collected will include event description, date of onset, assessment of severity and relationship to study product and alternate etiology (if not related to study product), date of resolution of the event, seriousness and outcome. The assessment of severity and relationship to the study product will be done only by those with the training and authority to make a diagnosis and listed on the Form FDA 1572 as the site Principal Investigator or sub-investigator. AEs occurring during the collection and reporting period will be documented appropriately regardless of relationship. AEs will be followed through resolution.

SAEs will be:

• Assessed for severity and relationship to study product and alternate etiology (if not related to study product) by a licensed study physician listed on the Form FDA 1572 as

the site Principal Investigator or sub-investigator.

- Recorded on the appropriate SAE report form, the medical record and captured in the clinical database.
- Followed through resolution by a licensed study physician listed on the Form FDA 1572 as the site Principal Investigator or sub-investigator.

For timeframe of recording adverse events, please refer to Section 6.1. All serious adverse events recorded from the time of first investigational product administration must be reported to the sponsor with the exception of any listed in Section 8.4.

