## 11.4.3 Related to Tissue Biopsy

Oral mucosal punch biopsy is a minor surgical procedure that may be associated with temporary bleeding, hematoma at the site, local infection and postoperative discomfort. These risks are small (generally <5%) and transient.

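### Adverse events from protocol procedures are captured inconsistently, because causality, sponsor reporting and follow-up collection are tied to the rinse

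*Combined protocol and SAP*

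**What the plan says.** **Causality.** Section 8.1.5: "All AEs will have their relationship to study product assessed using the terms: related or not related". Procedures are not mentioned.

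**Sponsor reporting.** Section 8.2: "All serious adverse events recorded from the time of first investigational product administration must be reported to the sponsor". For the period of adverse event recording, 8.2 refers to Section 6.1, which states no start or end.

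**Grade 1 events.** Section 6.1.1: "Grade I AEs will only be recorded if they are deemed possibly, probably or definitely related to the study intervention".

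**Follow-up.** Section 3.7: "Only adverse events at least possibly related to study treatment will be collected during the follow-up period".

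**Text pointing the other way.** Section 8.2 also says "AEs occurring during the collection and reporting period will be documented appropriately regardless of relationship", and asks for an alternate etiology when an event is not attributed to the product. Section 7.4 says "Serious adverse events potentially attributable to the study medication or procedures will be reported to IRB". The adverse event list in Appendix H takes in unexpected serious events related to the research as a whole.

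**The procedures.** A punch biopsy and an ACTH test are listed before treatment (3.3.1) and again at the end of treatment (3.3.3). Section 11.4.3 acknowledges the risk: "Oral mucosal punch biopsy is a minor surgical procedure that may be associated with temporary bleeding". It also lists hematoma, local infection and discomfort, and puts these risks generally below 5%.

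**The concern.** Section 11.5.1 describes the trial's risks as those of clobetasol and those of diagnostic procedures. Only the first has a causality question. The two biopsies also fall at the edges of the periods that the safety rules define: one before the first dose, one when dosing ends. A rule keyed to the rinse can miss an event from either.

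What is at stake is the trial's account of harm from procedures done partly for research. By 3.3.3 the day-28 biopsy serves marker development, while response is graded clinically. Eligibility (2.1.1.3) admits platelet counts down to 20,000/µL, and bleeding is one of the named biopsy risks. A sponsor overseeing such a trial would want to hear of a serious bleed from a baseline biopsy, and the final report should be able to separate biopsy harms from other events judged not related to the product.

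**Working it through.** The plan gives no figure on this point to reproduce. The check is to follow each kind of biopsy event through the rules.

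1. **Baseline biopsy, event before the first dose.** Appendix G places the biopsy in the window from day -7 to day 0 and marks no adverse event monitoring at baseline or day 0. Section 8.1.1 defines an adverse event in someone who has been given a product, and 6.1 supplies no recording start. A non-serious event may therefore go unrecorded. A serious one falls outside the sponsor rule in 8.2. It still goes to the IRB, because 7.4 names procedures and gives no start date.

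2. **Grade 2 or higher event during dosing.** This is documented under 8.2 whatever its cause, with an alternate etiology. The text does not lose it.

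3. **Event after the day-28 biopsy.** Section 3.7 counts follow-up from stopping the rinse, and 3.3.4 calls the 28 days after open-label treatment the follow-up period. On that usage the treatment-related filter applies directly after the biopsy, and a non-serious hematoma or infection a few days later would fail it. Serious events still go to the IRB under 7.4, and the sponsor rule in 8.2 has no end date.

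4. **Grade 1 event at any time.** Section 6.1.1 keeps it only if related to the intervention. Appendix G uses that word for the rinse, started on day 0 and completed on day 28. A Grade 1 biopsy event may therefore be dropped.

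5. **Causality scale.** Section 8.1.5 offers two terms. Sections 3.7 and 6.1.1 and Appendix H all filter on a possible relationship, a level that 8.1.5 does not provide.

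**Conflicts.** The filters in 3.7 and 6.1.1 contradict the rule in 8.2 that relationship does not matter. The product-only question in 8.1.5 does not fit the medication-or-procedure scope of 7.4 or the research-wide scope of Appendix H.

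**Scale of expected harm (not of unrecorded harm).**
- Section 11.1 expects over 80% adults. Taking 80% of the 34 evaluable patients: 0.80 × 34 = 27.2, say 27. Patients under 18 are left out because biopsy is not required for them.
- Two biopsies each: 27 × 2 = 54.
- At 5% per biopsy, the ceiling in 11.4.3: 54 × 0.05 = 2.7 expected; chance of at least one = 1 − 0.95^54 = 0.937.
- At 1% (an assumption): 54 × 0.01 = 0.54 expected; 1 − 0.99^54 = 0.419.
- With only 20 second biopsies, the number of pairs in the worked example of 10.2: 27 + 20 = 47 biopsies. At 5%, 2.35 expected and 1 − 0.95^47 = 0.910. At 1%, 0.47 expected and 1 − 0.99^47 = 0.376.

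The documents give no split by grade or timing, so the share that would go unrecorded cannot be computed.

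**The case against.** A reader might infer that biopsy harms go largely unrecorded, or that the trial could not report them. The documents do not support that. Section 8.1.5 assigns attribution and excludes nothing. Section 8.2 documents events in the collection period regardless of cause and asks for an alternate etiology, where a biopsy could be entered. Section 7.4 and Appendix H reach serious events from procedures or from the research, and 7.3 covers deaths within 30 days of a research intervention, other than those from progressive disease. Section 8.3 requires expedited SAE submission and states no start date. Those points stand, and they confine the gap to the cases traced above.

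They do not close it. The rule in 8.2 operates inside a period that is never defined. Alternate etiology helps only for events already recorded. Section 7.4 concerns serious events to the IRB. Appendix H is limited to unexpected serious events, and bleeding or infection listed in 11.4.3 might be judged expected. Section 8.3, silent on a start, leaves the explicit one in 8.2 unresolved.

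It is also fair to say that the reach of 3.7 is ambiguous. Its filter sits in a paragraph about three-monthly contacts, Appendix G marks adverse event monitoring at days 28 and 56, and 3.8 asks for a safety visit about 30 days after the last dose. Loss of events between days 28 and 56 is therefore possible on the wording, not certain. The number of biopsies is uncertain too: the day-28 biopsy is required in 10.2 but marked optional in Appendix G, baseline evaluation may be done under another protocol (3.3.1), and patients who continue the rinse directly enter follow-up later. Finally, limiting Grade 1 recording can be a deliberate choice. The difficulty is that its test looks to the rinse.

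**Conclusion.** The point holds as an inconsistency with limited but real consequences. As written, a serious biopsy event before dosing need not reach the sponsor, although it reaches the IRB. Three groups may go unrecorded: non-serious events from the baseline biopsy before dosing, non-serious events after the day-28 biopsy, and Grade 1 biopsy events. The second group rests on reading follow-up as 3.3.4 does; the third rests on reading the intervention as the rinse, as Appendix G does. Expected harms run from about 0.5 to 2.7 over 47 to 54 biopsies at assumed risks of 1% to 5%. These figures show only that biopsy events are plausible in a trial of this size, and they do not measure loss. No treatment comparison, endpoint or sample size is affected.

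**What to change.** - **8.2 and 6.1:** state one window for AE and SAE recording and for sponsor reporting, starting at the first procedure done under this protocol. Put it in 6.1, where 8.2 already sends the reader.
- **3.7 and 6.1.1:** change *study treatment* and *study intervention* to *study treatment or procedures*, at least through the day 56/70 visit.
- **8.1.5 and the AE form:** record relationship to procedures (biopsy, ACTH test, blood draw) as well as to the product.
- **8.1.5, 3.7, 6.1.1 and Appendix H:** use a single causality scale, so that every filter refers to a level the form offers.

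The cost is these wording changes, one extra field, and a few more minor events to record. An alternate etiology entry could partly serve as the procedure field, but a dedicated field makes the events countable.

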## 8.2 Assessment of Safety Events

AE information collected will include event description, date of onset, assessment of severity and relationship to study product and alternate etiology (if not related to study product), date of resolution of the event, seriousness and outcome. The assessment of severity and relationship to the study product will be done only by those with the training and authority to make a diagnosis and listed on the Form FDA 1572 as the site Principal Investigator or sub-investigator. AEs occurring during the collection and reporting period will be documented appropriately regardless of relationship. AEs will be followed through resolution.

SAEs will be:

• Assessed for severity and relationship to study product and alternate etiology (if not related to study product) by a licensed study physician listed on the Form FDA 1572 as

the site Principal Investigator or sub-investigator.

- Recorded on the appropriate SAE report form, the medical record and captured in the clinical database.
- Followed through resolution by a licensed study physician listed on the Form FDA 1572 as the site Principal Investigator or sub-investigator.

For timeframe of recording adverse events, please refer to Section 6.1. All serious adverse events recorded from the time of first investigational product administration must be reported to the sponsor with the exception of any listed in Section 8.4.

## 8.3 **Reporting of Serious Adverse Events**

Any AE that meets protocol-defined serious criteria or meets the definition of Adverse Event of Special Interest that require expedited reporting must be submitted immediately (within 24 hours of awareness) to OSRO Safety using the CCR SAE report form. Any exceptions to the expedited reporting requirements are found in Section **8.4**.

All SAE reporting must include the elements described in Section 8.2.

SAE reports will be submitted to the Center for Cancer Research (CCR) at: [contact] and to the CCR PI and study coordinator. CCR SAE report form and instructions can be found at: https://nih.sharepoint.com/:u:/r/sites/NCI-CCR-OCD- Communications/SitePages/Forms-and-Instructions.aspx?csf=1&web=1&e=uWBXtI

Following the assessment of the SAE by OSRO, other supporting documentation of the event may be requested by the OSRO Safety and should be provided as soon as possible.

## 8.4 REGULATORY REPORTING FOR STUDIES CONDUCTED UNDER CCR-SPONSORED IND

Following notification from the investigator, CCR, the IND sponsor, will report any suspected adverse reaction that is both serious and unexpected. CCR will report an AE as a suspected adverse reaction only if there is evidence to suggest a causal relationship between the study product and the adverse event. CCR will notify FDA and all participating investigators (i.e., all investigators to whom the sponsor is providing drug under its INDs or under any investigator's IND) in an IND safety report of potential serious risks from clinical trials or any other source, as soon as possible, in accordance to 21 CFR Part 312.32.

## 8.5 SPONSOR PROTOCOL DEVIATION REPORTING

A Protocol Deviation is defined as any non-compliance with the clinical trial Protocol, Manual of Operational Procedures (MOP) and other Sponsor approved study related documents, GCP, or protocol-specific procedural requirements on the part of the participant, the Investigator, or the study site staff inclusive of site personnel performing procedures or providing services in support of the clinical trial.

It is the responsibility of the study Staff to document any protocol deviation identified by the Staff or the site Monitor in the CCR Protocol Deviation Tracking System (PDTS) online application. The entries into the PDTS online application should be timely, complete, and maintained per CCR PDTS user requirements.

In addition, any deviation to the protocol should be documented in the participant's source records and reported to the reviewing IRB per their guidelines. OSRO required protocol

deviation reporting is consistent with E6(R2) GCP: Integrated Addendum to ICH E6(R1): 4.5 Compliance with Protocol; 5.18.3 (a), and 5.20 Noncompliance; and ICH E3 16.2.2 Protocol deviations.

## 9 CLINICAL MONITORING

As a sponsor for clinical trials, FDA regulations require the CCR to maintain a monitoring program. The CCR's program allows for confirmation of: study data, specifically data that could affect the interpretation of primary and secondary study endpoints; adherence to the protocol, regulations, ICH E6, and SOPs; and human subjects protection. This is done through independent verification of study data with source documentation focusing on:

- Informed consent process
- Eligibility confirmation
- Drug administration and accountability
- Adverse events monitoring
- Response assessment.

The monitoring program also extends to multi-site research when the CCR is the coordinating center.

This trial will be monitored by personnel employed by a CCR contractor. Monitors are qualified by training and experience to monitor the progress of clinical trials. Personnel monitoring this study will not be affiliated in any way with the trial conduct.

## **10 STATISTICAL CONSIDERATIONS**

## **10.1 SUBJECT ACCRUAL**

Subjects of both sexes, from all racial and ethnic groups are eligible for this trial if they meet the criteria outlined in Section 2.1. To date, there is no information that suggests differences in drug metabolism or disease response among racial or ethnic groups or between the two sexes, indicating that results of the trial will be applicable to all groups. Efforts will be made to extend the accrual to a representative population, but achievement of a fully representative subject population is unlikely in a pilot study with limited accrual.

## **10.2** STATISTICAL CONSIDERATIONS

The primary objective of this randomized pilot study is to determine if the use of clobetasol may result in improvement or stabilization in outcomes in patients with oral chronic GVHD. An important secondary objective is to preliminarily validate and explore the utility of the response measurement instruments.

Patients with oral cGVHD meeting the eligibility criteria will be separately randomized to either 1 month of clobetasol 0.05% oral rinse or placebo; there will not be separate accrual goals for each age group or type of underlying disease. The patients will be followed every 2 weeks for 1 month for their primary endpoint, and once 1 month after completion of study agents.

The primary endpoint will be the change in OMRS score (**Appendix A**) after 1 month of clobetasol 0.05% oral rinse compared to baseline. We will consider a 25% or larger decrease in the score to be clinically significant and a 'response' for the purpose of this study. As this is a pilot study, the association between this level of change and other scales will also be assessed to determine if this is a meaningful measure to use in future trials or if modification is warranted. Thus, this study will be a pilot for the determination of a meaningful response as well for determining if the agent tested may be beneficial.

After the first 2 weeks of clobetasol treatment, patients can be removed from study if oral disease progression is documented. Patients who are taken off study for oral disease progression will be counted as non-responders at the time of the final analysis. Patients taken off study for non-compliance, specifically  $\geq$ 75% non-use of the oral rinse, will not be included in the data analysis

The patients enrolled on this study may be a very heterogeneous group with respect to prior treatments, extent of disease, etc. Patients taken off study for reasons unrelated to the primary outcome will be classified as non-responders and analyzed accordingly. The results will be interpreted in the context of a pilot study with potential limitations noted.

This study will aim to enroll a total of 34 evaluable patients randomized in a 1:1 fashion (17 per arm) to receive clobetasol rinse or placebo. The initial phase of the study will involve two weeks of either clobetasol rinse or placebo. At the end of the initial 2 weeks, patients receiving placebo will receive 28 days of clobetasol while those receiving clobetasol initially will receive an additional 14 days of clobetasol. Thus, each group will receive 28 days of clobetasol following either a 14 day placebo or immediately after randomization.

Patients will be randomized with a single stratification factor to try to ensure a balanced distribution among those getting placebo or not initially: being identified as having a high intensity of immunosuppression (2 or more agents/modalities  $\pm$  prednisone $\geq$ 0.5 mg/kg/day) vs. no or a lesser intensity of systemic immunosuppression according to the Intensity of Immunosuppression Scale . This scale was developed using expert opinion, and has been preliminarily demonstrated to have predictive validity as measure of the intensity of systemic immunosuppression. A low intensity regimen is defined as treatment with prednisone alone at a dose of less than 0.5 mg per kilogram per day. Moderately intense regimens include single agent prednisone at a dose greater than or equal to 0.5 mg per kilogram per day, and/or any other single agent or modality. Regimens comprised of two or more agents or modalities (+/- prednisone greater than or equal to 0.5 mg per kilogram per day), are categorized as highly intensive systemic immunosuppression. When scoring the intensity of systemic immunosuppression, the use of topical agents is not captured.

The primary endpoint is the fraction of subjects who experience a 25% improvement in their OMRS compared to their own baseline. The fraction will be estimated with a two-tailed 95% confidence interval as the primary outcome. This will be done using all 34 patients together provided that the changes from baseline to day 28 for the two groups are sufficiently similar. A formal test will be performed assess their comparability. This will be determined conservatively, by obtaining the actual difference in the individual OMRS for each patient at baseline (day 0 for initial clobetasol and day 14 for those initially given placebo) vs. the value after day 28 of clobetasol and comparing those differences between the two randomized groups using a two-tailed Wilcoxon rank sum test. If the p-value for that comparison is >0.30, then the two groups will be considered sufficiently similar to allow pooling of the results and to report a combined

fraction of patients who have a 'response' to 28 days of clobetasol. In this case 34 patients will be sufficient to allow the proportion of patients with a response of 75% or more to have a two-sided 95% confidence interval of +/- 15% or less, which will be considered sufficiently precise. Fractions of responses <75% would have slightly wider confidence interval widths.

An important secondary endpoint is to compare the changes from day 0 in the OMRS until day 14 between those who only receive placebo by that point vs. those who received clobetasol. This evaluation will be done both with respect to the fraction with a response by 2 weeks, as well as comparing the actual changes in OMRS from day 0 to day 14.

By enrolling 17 patients per arm, a 0.10 alpha level one-tailed Fisher's exact test will have 80% power to detect a difference between a potential 75% of patients having a 25% or greater decrease in severity score on the clobetasol arm and about half that amount, 35%, on the placebo arm. A one-tailed test is sufficient for this secondary objective in this study since we will not expect clobetasol to be associated with a lower fraction of patients with benefit compared to placebo and because this is intended to be a pilot study to determine if a potential trend of magnitudes anticipated, but not necessarily a statistically significant gain, may be detected. Should very promising results be obtained, then a subsequent trial could be conducted to build upon and further confirm the benefit noted.

A comparison of the actual levels of changes in the oral severity score between the arms will also be done using a Wilcoxon rank sum test as a secondary analysis. With 17 patients per arm, there is approximately 80% power to detect a difference between the arms in the changes from baseline to day 14 equal to one standard deviation of the change (effect size=1.0), using a two-tailed Wilcoxon rank sum test with a 0.05 significance level.

All patients will be placed on clobetasol for one month, whether following a two-week period with placebo or beginning at the time of randomization. In addition, comparisons between actual oral severity scores at the beginning of this period and one month later will be made using a paired t-test, or using a Wilcoxon signed rank test if the differences are not normally distributed (p<0.05 by Shapiro-Wilks test). These results will be evaluated separately according to the randomized treatment arm as well as overall if the changes in score according to the randomized assignments are similar (p>0.30 for Wilcoxon rank sum test comparing changes in scores between the two arms over the one month clobetasol period). Although this would also be considered a secondary evaluation, there would be 82% power to identify a 0.75 standard deviation change to be significant with a two-tailed 0.05 alpha level paired t-test if all 17 patients are available within each arm for this comparison.

Patients will undergo oral mucosa biopsies at the beginning of the study, and many are expected to have biopsies at the end of 28 days of treatment. Although required, these biopsies may not be obtained on all patients, and the number of patients with paired data will determine the differences in immunologic parameters from the biopsies that can be detected. For example, if there were 20 patients with paired biopsy data and 5 immunologic parameters of interest, each one would have 93% power to detect a change with an effect size of 1.0, with a very conservative two-tailed 0.01 significance level, to account for multiple comparisons. Fewer than 20 patients with paired biopsies would reduce the power accordingly, but since this is a secondary objective, the results of these tests will be presented in the context of an exploratory study.

At a rate of 1 patient per 2 weeks accrual, approximately 16 to 20 months will be required to meet the accrual goal of 34 evaluable patients. To allow for a small number of inevaluable patients, the accrual ceiling will be set at 40 patients.

